## **Exercise Compliance**

The Exercise Adherence Rating Scale (EARS), which evaluates exercise compliance, will be administered 2 times to determine change at eight weeks and third month. This scale consists of 3 parts: A, B, C. Section A, consists of 6 items not included in the scale scoring. Section B consists 6 items, and every item have five point likert scale and describes how to do the recommended home exercise. Minimum point for this section 0, and maximum point is 24. The higher score shown exercise adherence is high. Section C is the section that evaluates the reason for the absence of compliance with the recommended home exercise and contains 10 items, every item have five point likert scale. Sections are calculated to result in a possible score between 0 and 40. The higher score shown exercise adherence is high.

Also, patients will be questioned with Visual Analog Scale in every session and at 3 months after treatment if he / she is doing home exercises. For the Visual Analog Scale, a horizontal line of 10 centimeters on A4 paper will be used. Most right point of the scale represents "I've never done my exercise." while most left point of the scale "I've done all my exercise.". The patient will be asked to mark the appropriate place.

## **Learning Forms**

The following question will be used to classify the learning styles of people exercising. Although there are scales that question academic learning styles, there is no scale that questions a new skill learning. Based on the previously developed scales, the following question was formed.

What do you do first to learn a new job (eg, cooking, changing a car tire, a dance figure)? (Please give the number of the routes you use in order of priority.)

- I follow the maker, ask someone to show them or look at the picture books (This option questions the use of visual strategy)
- I try it myself, I try to do this (This option questions the use of motion kinesthetic senses)
- I would like someone to tell (this option questions the use of auditory senses)

## **Item 7a. How sample size was determined**

For the calculation, version 2.9.1.2 of the G \* Power software was used (14). The preliminary (a priori) power calculation protocol, the effect size for the pain variable, was calculated as 1.23 based on a study by Amit et al (15). Type I error probability was 0.05 and power was accepted as 0.80. The distribution rate of groups 1 is assumed. As a result, the number of people to be taken for each group is calculated as 12. Assuming that the loss of patients during the treatment will be 10%, it is expected to complete the study with 30 patients in total.

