## **Item 6a. Completely defined pre-specified primary and secondary outcome measures, including how and when they were assessed**

### **Evaluation of the severity of pain:**

Visual Analog Scale will be used before the treatment, at before and after every treatment session and at the third month after the treatment. This scale is a 100 millimeter line drawn horizontally on an A4 sheet of paper. The left end of the line shows “no pain at all”, the right end shows “my pain is as bad as it could be”, while the remaining part shows the intermediate values. The patient is asked to mark the severity of the pain on the chart. Validity and reliability were made. The minimal clinical significance difference in chronic low back pain was 20 millimeters.

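### Later pain readings depend on attending sessions or finishing treatment, and no analysis population or missing-data rule is given, so early stoppers are likely to leave the comparison and may bias it in either direction

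*Combined protocol and SAP*

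**What the plan says.** Four parts of the combined protocol and SAP bear on this point.

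- **Timing of pain (Item 6a, severity of pain).** The "Visual Analog Scale will be used before the treatment, at before and after every treatment session and at the third month after the treatment". No end-of-programme visit is named separately from the last session.
- **Timing of adherence (Item 6a, Exercise Compliance).** For home exercise, "patients will be questioned with Visual Analog Scale in every session and at 3 months after treatment". The Exercise Adherence Rating Scale (EARS) "will be administered 2 times to determine change at eight weeks and third month", with no statement of what the eight weeks are counted from. The disability and walking sections give no assessment times. The progress-rate section records each patient's programme length in days.
- **Sample size (Item 7a).** For a standardised effect on pain of 1.23, "the number of people to be taken for each group is calculated as 12". The allowance for loss follows: "Assuming that the loss of patients during the treatment will be 10%, it is expected to complete the study with 30 patients in total". Loss is not defined.
- **Analysis (Item 12a).** An ANOVA with between-group and within-group terms is named. There is no analysis population, no statement that patients are analysed as randomised and no method for missing values. It does not say which time points enter the model.

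**The concern.** Take a patient who attends 6 of the 16 sessions and then stops. Pain is recorded at those 6 sessions and not afterwards. The follow-up reading is dated from the end of treatment, which for this patient is either undefined or falls earlier than for patients who finish. No section asks for this patient to be assessed later, or for the reason for stopping to be recorded. A conventional repeated-measures ANOVA omits anyone who lacks one of the time points in the model, so the likely result is a comparison of completers.

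Stopping could plausibly depend on the arm. Item 2a argues that the complexity of these exercises lowers adherence, and Item 5 makes the way they are taught the sole contrast between the groups. If teaching affects who persists, a completers' comparison no longer compares the groups as randomised. Pain is the variable on which the trial is sized. A reading that was never taken cannot be recovered at analysis.

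**Working it through.** **1. The plan's own figures.** Inputs from Item 7a: d = 1.23, type I error 0.05, power 0.80, equal groups. A two-sided two-sample t-test (noncentral t) needs 12 per group: power is 0.821 at 12 and 0.783 at 11. The stated 12 is reproduced. Allowing for 10% loss, 12/0.9 = 13.3, so 14 per group or 28 in total. The stated 30 is close to this and equals three blocks of 10. Ten per cent of 30 is 3 patients.

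**2. Power is not the problem.** At d = 1.23, power is 0.85 with 13 per arm, 0.88 with 14 and 0.90 with 15. The question is bias.

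**3. Size in millimetres, under assumed changes.** The documents give no pain changes for completers or stoppers. Assume −20 mm in completers of both arms, +20 mm in stoppers and 15 randomised per arm. With k stoppers in an arm:

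mean of all randomised = [(15 − k) × (−20) + k × 20] / 15

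- k = 1: (−280 + 20)/15 = −17.3 mm; completers look 2.7 mm too good.
- k = 2: (−260 + 40)/15 = −14.7 mm; 5.3 mm too good.
- k = 3: (−240 + 60)/15 = −12 mm; 8 mm too good.

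Net bias in the difference between arms:

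- 2:1 split: 5.3 − 2.7 = 2.7 mm before rounding, or 2.7/20 = 13% of the important difference stated in Item 6a.
- 3:0 split: 8 − 0 = 8 mm, or 8/20 = 40%.

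If stopping has nothing to do with arm, all three fall in one arm with probability 2 × C(15,3)/C(30,3) = 910/4060 = 22%. The other 78% are 2:1 splits.

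The bias is (difference in number of stoppers) × (gap between stoppers and completers)/15. The gap above is 40 mm. A gap of 20 mm halves the results, to 1.3 mm and 4 mm. A gap of the opposite sign, where patients stop because they improved, reverses them.

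**4. Size in SD units, by simulation.** 50,000 runs, 15 per arm, no true difference, completers-only t-test. The nominal rate of false significant results in favour of the arm with more stoppers is 2.5%.

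| Assumed link between stopping and worse pain | 2 v 1 lost: bias; false favourable | 3 v 0 lost: bias; false favourable |
|---|---|---|
| Stoppers are exactly the worst | 0.11 SD for; 6.6% | 0.33 SD for; 15.4% |
| Correlation 0.5 | 0.05 SD for; 3.8% | 0.16 SD for; 6.3% |
| None | 0; 2.4% | 0; 2.6% |
| Correlation −0.5 (stop when improved) | 0.05 SD against; 2.1% | 0.16 SD against; 1.0% |

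"For" and "against" refer to the arm with more stoppers. With one lost in each arm for the same kind of reason, the difference is unbiased. The documents give no SD, so these figures cannot be converted to millimetres.

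**The case against.** A reader might infer that the plan counts patients who stop sessions as lost and removes them. It does not say so. The sentence in Item 7a is an allowance in a sample-size calculation, and Item 12a is silent on who is analysed. Exclusion is an inference. It is a reasonable one, because extra patients are needed only if those lost do not count towards the 12 per group, and because the named ANOVA ordinarily needs complete records.

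A reader might also infer that the arm with more stoppers will look better. That requires unequal stopping, a link with worse pain and a completers-only analysis, all at once. The bias reverses if patients stop because they have improved, and vanishes if losses are unrelated to pain or are balanced in number and reason.

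Early stoppers are not without data. They keep every session reading already taken, and EARS has an eight-week point. EARS Section C asks why home exercise was not done, which touches on tolerability but not on why sessions stopped. The 8 mm figure is the extreme split under one assumed pair of changes, and chance imbalance favours neither arm on average.

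These objections stand and limit the claim. They do not supply a comparable later pain value for the patient who stops.

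**Conclusion.** The concern holds as a gap in data collection and analysis that leaves the pain comparison open to selective loss. Run as written, the plan provides no end-of-programme or three-month pain value for an early stopper that can be set beside the others', and no rule keeps that patient in the analysis. With 3 of 30 lost, the illustrative net bias runs from nil through 2.7 mm (2:1) to 8 mm (3:0), in either direction. It rests on the assumed 40 mm gap, on analysis of completers only, and on taking the difference between all patients as randomised as the quantity of interest. The documents support neither a prediction of which arm would gain nor the statement that stoppers are formally excluded.

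**What to change.** - **Item 6a.** Invite every randomised patient to an end-of-programme and a three-month assessment whether or not sessions were completed. For early stoppers, date both from when their programme was scheduled to end, counted from randomisation. The protocol must state that scheduled end, and the time origin of the eight-week EARS visit.
- **Records.** Note the session number and reason for stopping, and report both by arm. In Item 7a, separate stopping sessions from loss to follow-up, and say whether 30 means enrolled or completing; 30 completers at 10% loss would need 30/0.9, or 34 enrolled.
- **Item 12a.** Analyse all randomised patients as assigned, with a method that keeps incomplete records, for example a mixed model for repeated measures, in place of an ANOVA that drops them. Name the time points in the model and add a sensitivity analysis for missing values.

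The cost is a few extra contacts for about 3 patients and slightly more analysis work. The estimated difference may move in either direction. Re-dating everyone's follow-up from randomisation would change the interval since treatment for all patients, so the special dating is best confined to those who stop early.

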## **Item 8a. Method used to generate the random allocation sequence**

We used sequentially numbered, opaque sealed envelopes (SNOSE), for randomization with block size 10 and allocation ratio 1:1. Participants will be enrolled to the study by MD [name], and assigned to the intervention by [name] with use of SNOSEs.

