## **Methods**

### **Item 3a. Description of trial design (such as parallel, factorial) including allocation ratio**

This will be a block randomized (Block number was 10.), allocation ratio 1:1, assessor blinded, controlled, parallel-group study conducted in the Hacettepe University, Turkey.

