## **Item 4b. Settings and locations where the data were collected**

This study will carry out at the Back and Neck Health Unit at Hacettepe University Faculty of Physiotherapy, Ankara, Turkey. Anticipated data collection date between June 2019 and September 2019.

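### One fixed block size of 10, with no safeguard stated, would leave on average 5 of 30 allocations deducible by anyone who knows the size and tracks past assignments

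*Combined protocol and SAP*

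**What the plan says.** Item 8a gives one block size: "randomization with block size 10 and allocation ratio 1:1", with opaque sealed envelopes used in number order. Item 3a describes the trial as "block randomized (Block number was 10.), allocation ratio 1:1". Taken literally, that would be ten blocks of three among 30 patients, which cannot be 1:1, so it can only mean size 10.

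Item 7a says "it is expected to complete the study with 30 patients in total". Item 4b places the trial in one setting, the "Back and Neck Health Unit at Hacettepe University Faculty of Physiotherapy". Under Item 5 the arms differ only in how the exercises are taught (physiotherapist with pictures, or animated video), so the treating physiotherapist knows the arm. Blinding in Items 3a and 11a is confined to the assessor.

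Item 8a gives enrolment to a physician ("Participants will be enrolled to the study by MD") and describes assignment by envelope as a separate task. No item mentions varied block sizes, withholding the size from staff, keeping past allocations from the enrolling physician, or who prepared the list.

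**The concern.** In a balanced block of 10, once one arm has its five patients the rest of the block is determined. A person who knows the size and has seen the earlier assignments then knows the next arm before the envelope is opened.

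Foreknowledge at enrolment is how selection bias enters a randomised trial. There is room for it here: two criteria in Item 4a, computer literacy and prior knowledge of motor control exercises, have no stated threshold, and the first plausibly bears on how a patient would do with video teaching. Pain, on which the trial is powered, is marked by the patient, and disability and adherence are questionnaires. With about 15 patients per arm, a few steered enrolments could shift a mean.

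**Working it through.** **Inputs.** Block size 10, so m = 5 per arm per block (Item 8a). Ratio 1:1 (Items 3a, 8a). Total 30 (Item 7a), taken as 30 randomised in three complete blocks.

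**The plan's own figure.** The documents give no figure for predictability. The sample size reproduces: effect size 1.23, two-sided 0.05 and power 0.80 need 11.42, hence 12 per group. Allowing 10% loss, 12/0.9 = 13.3, so 14 per group or 28 in all. The stated 30 is two more and makes three blocks of 10.

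**Certain allocations, size known.** These are the final run of identical assignments in each block. The expected length is 2m/(m+1) = 10/6 = 1.667 per block, and 3 × 1.667 = 5.0 of 30, or 16.7%. Enumerating all C(10,5) = 252 balanced blocks agrees. Over three blocks the number is at least 3 and at most 15; the chance of exactly 3 is 0.17, of 5 or more 0.57, and of 8 or more 0.07.

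**If 30 means completers.** 30/0.9 = 33.3, so about 34 randomised: three blocks and four patients of a fourth. No arm can reach five within four patients, so the expectation stays 5.0, now of 34 (15%).

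**Best guess for every patient.** Always guessing the arm with fewer so far needs no knowledge of block size. Expected correct guesses per block are m + (4^m / C(2m,m) − 1)/2.
- m = 5: 5 + (1024/252 − 1)/2 = 6.532; three blocks give 19.60.
- m = 4, 5, 6 (blocks of 8, 10, 12): 5.329 + 6.532 + 7.716 = 19.58.

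Chance alone gives 15.

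**Like-for-like comparison.** Each observer has the full allocation history. The 2.3 comes from simulating 20,000 lists with one block each of 8, 10 and 12 in random order. The second row is the expected final run of the last block: 10/6 for three 10s, and (8/5 + 10/6 + 12/7)/3 for the varied scheme.

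| Observer also knows | Three blocks of 10 | 8, 10, 12 in random order |
|---|---|---|
| The sizes, but not their order | 5.0 | about 2.3 |
| Only that the list ends at 15:15 | 1.67 | 1.66 |

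**Smaller fixed blocks are worse.** By the same formula, a known size of 6 gives 1.5 × 5 = 7.5 of 30 certain, and a known size of 4 gives 1.333 × 7.5 = 10 of 30.

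**The case against.** The strongest reply is that 10 is already a large block for 30 patients, that varying it leaves the best-guess rate at 19.6, and that the person able to bias entry is the enrolling physician, whom nothing in the documents shows seeing treatments, keeping a tally or knowing where blocks begin. Much of this stands. Ten is better than a smaller fixed block, and a mix of 4s and 6s would raise the best-guess rate to between 20.6 and 20.8. The second row of the table also shows that much of the gain comes from not disclosing the size, whichever scheme is used. What remains is that the size is stated, nothing withholds it or the allocation history from the enroller, and certainty is a stronger lever than a better-than-even guess.

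A reader might infer four stronger things that the documents do not support:
- **That staff know five allocations.** This holds only for someone who knows the size and tracks every assignment; the documents neither show it nor rule it out.
- **That the size was public during enrolment.** The document is an ethics-approved protocol with no registration number yet assigned; nothing shows who could read it.
- **That varied blocks leave nothing certain.** Anyone who knows the list ends at 15:15 can still deduce the final run.
- **That Items 3a and 8a describe different schemes.** Only a block size of 10 fits both, so this is a wording slip.

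**Conclusion.** The point holds as a minor, inexpensive improvement. With one fixed block size of 10, an observer who knows the size and has followed past allocations would be certain of 5.0 of 30 assignments on average (17%, minimum 3), and sealed envelopes do not prevent that deduction. The figure assumes 30 randomised in three complete 1:1 blocks.

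Separate enrolment and assignment reduce the risk. With no safeguard stated for the size or the allocation history, they do not remove it. It is a risk of selection bias; nothing in the documents indicates that bias occurred.

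**What to change.** Before enrolment, have someone who neither enrols nor treats generate the list with blocks of 8, 10 and 12 in random order. Extend it beyond 30 if 30 means completers, since about 34 envelopes would then be needed. Keep the sizes and their order out of documents available to enrolling and treating staff. In Items 3a and 8a, write *permuted blocks of varying size*, which also removes the wording slip.

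The document was last revised in July 2018 and anticipates data collection from June 2019, so by its own dates the change can precede enrolment.

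The cost is a new envelope list, two wording changes, a possible mid-trial imbalance of 6 instead of 5, and a small final imbalance if an extended list stops mid-block. The gain is fewer certain allocations; overall guessability does not change.

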## **Item 11a. If done, who was blinded after assignment to interventions (for example, participants, care providers, those assessing outcomes) and how**

The patient's group will not be written on the evaluation paper, so they will be kept from researcher [name].

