## **Item 5. The interventions for each group with sufficient details to allow replication, including how and when they were actually administered.**

Conventional treatment will be applied to both groups. Conventional treatment includes application of superficial temperature, soft tissue relaxation techniques and joint mobilizations. Only difference between groups will be exercise teaching methods. Each patient will receive an equal session routine physiotherapy treatment and the treatment will take an average of 60 minutes. On the other hand, individualization of the program will be done according to the criteria of transition to upper exercise, and it will be recorded when each patient has a higher exercise.

The exercise program will be performed according to the protocol of Hicks et al. And no medical device will be used.

The exercise program which will be use in the study for both groups (10,11):

First Session:

- Patient will be watch a pain physiology multimedia video prepared by study team. If patient have a question after watching the video, will be encouraged to ask her physiotherapist.
- The anatomy and kinesiology of the trunk stabilization, and motor control exercise principles will be explained to patient. For this purpose, face-to-face group receive information from physiotherapist with help of pictures while multimedia learning group watch a video with animations and narrations prepared by study team and reviewed by a specialist team.

2-16. seasons:

- Exercises Program
  - Transversus abdominus (30 repetitions with 8-s hold)
    - Abdominal Draw-in Maneuver (30 repetitions with 8-s hold)
    - Abdominal Draw-in Maneuver + heel slides (30 repetitions with 8-s hold)
    - Abdominal Draw-in Maneuver + leg lifts (20 repetitions with 8-s hold)
    - Abdominal Draw-in Maneuver + bridging (20 repetitions with 8-s hold, then progress to 1 leg)
    - Abdominal Draw-in Maneuver + standing (30 repetitions with 8-s hold)
    - Abdominal Draw-in Maneuver + standing row exercise (20 repetitions per side with 6-s hold)
    - Abdominal Draw-in Maneuver + walking (30 repetitions with 8-s hold)
  - Paraspinals/multifidi
    - Abdominal Draw-in Maneuver + Quadruped arm lifts (30 repetitions with 8-s hold)
    - Abdominal Draw-in Maneuver + Quadruped leg lifts (30 repetitions with 8-s hold)
    - Abdominal Draw-in Maneuver + Quadruped alternate arm and leg lifts (30 repetitions with 8-s hold)
  - M. Quadratus lumborum and m. obliquus abdominis

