### **Evaluation of Disability**

Disability will be evaluated by Oswestry Disability Scale 2.0 Turkish version. This version contains 10 multiple-choice questions that question how low back pain affects a person in his or her daily life. Each question has 6 options. As the disability increases, the score of each problem increases. In the worst case you can get 50 points. The last point is the patient's score 100.

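### The assessor-blinded label does not blind the rater of pain, disability and adherence, who is the patient, and the one stated measure does not stop patients disclosing their group to the assessor

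*Combined protocol and SAP*

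**What the plan says.** - **Label.** Item 3a describes the trial as an "assessor blinded, controlled, parallel-group study". It does not limit the description to particular outcomes.
- **Method.** Item 11a is the only text on how blinding is achieved. It says that the patient's "group will not be written on the evaluation paper, so they will be kept from researcher" (the name is removed). Its heading asks about participants, care providers and assessors; the answer does not mention the first two.
- **What differs between arms.** Item 5 says: "Only difference between groups will be exercise teaching methods". In the first session the "face-to-face group receive information from physiotherapist with help of pictures while multimedia learning group watch a video with animations and narrations".
- **Pain (Item 6a).** "The patient is asked to mark the severity of the pain on the chart". On timing: "Visual Analog Scale will be used before the treatment, at before and after every treatment session", and again three months after treatment.
- **Disability (Item 6a).** This is the Oswestry: "This version contains 10 multiple-choice questions that question how low back pain affects a person in his or her daily life". How it is administered is not stated.
- **Adherence (Exercise Compliance).** The EARS is given at eight weeks and at the third month. In addition, "patients will be questioned with Visual Analog Scale in every session" and at three months, and they mark that scale themselves.
- **Walking and progress.** The 6-minute walk and the OptoGait variables are measured by test or device. Progress rate is taken from the recorded dates of moving up an exercise.
- **Sample size (Item 7a).** The calculation uses the pain variable. No outcome is named as primary.

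**The concern.** Blinding an assessor protects an outcome to the extent that the assessor's judgement or conduct determines the recorded value. Where the patient supplies the value, what matters is what the patient knows, and here the patient knows the teaching method. Someone who reads the Item 3a label without the outcome list could take the pain and adherence results as protected from the rater's expectations when they are not. This matters most for pain, on which the trial is sized, and for adherence, which the rationale in Item 2a puts at the centre of the argument for multimedia teaching.

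The second weakness concerns the masked researcher. Leaving the group off a form removes one route by which that person could learn it. It does not close the obvious other route, a patient talking about the video or about the physiotherapist's explanation. If that happens, the walk and gait tests lose their protection as well.

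**Working it through.** **Step 1. Who supplies each value, and what masking a researcher can do for it.** The instruments are those listed from Item 6a through Exercise Compliance.

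| Instrument | Who supplies the value | What a masked researcher can protect |
|---|---|---|
| Pain VAS | Patient marks the line | Handing out and measuring the form |
| Oswestry | Patient's answers | Prompting and scoring |
| EARS | Patient's answers | Prompting and scoring |
| Home-exercise VAS | Patient marks the line | Questioning and measuring the form |
| 6-minute walk | Patient's performance, run by a tester | Conduct and recording, if masking holds |
| OptoGait variables | Device | Conduct, if masking holds |
| Progress rate | Dates of moving up an exercise | Not stated who decides or records |

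Counted by instrument, 4 of 7 depend on the patient's own report. Counted by the protocol's outcome headings (pain, disability, walking, progress, compliance), it is 3 of 5.

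**Step 2. Does the patient know the arm?** The protocol does not say so in words, but it follows from Item 5: one arm is taught in person with pictures, the other by an animated, narrated video. Whether patients know which method is expected to do better is not stated.

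**Step 3. What stands between the patient's knowledge and the masked researcher?** Item 11a offers only the omission of the group from the form. No section tells patients not to disclose, says who hands out or collects forms, or says who is present when they are completed. The sealed envelopes in Item 8a conceal the allocation until it is assigned; they do nothing for assessments made afterwards.

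**Step 4. Is pain really the sizing outcome?** Inputs from Item 7a: standardised effect d = 1.23, alpha 0.05, power 0.80, equal groups. Two-sided testing is my assumption, as the plan does not say. For a two-sample t test, df = 2n − 2, the noncentrality is d × √(n/2), and power comes from the noncentral t distribution.
- n = 11: 1.23 × √5.5 = 2.88, power 0.783.
- n = 12: 1.23 × √6 = 3.01, power 0.821.

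The plan's 12 per group is therefore reproduced, on pain. Allowing for 10% loss, 12 / 0.9 = 13.3, so 14 per arm or 28 in total. The stated 30 is close to this and equals three blocks of 10. The blinding point does not alter these figures.

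**Step 5. Illustration only.** The documents give no bias figure. Assume no true difference in pain, and that unblinded reporting shifts one arm relative to the other by b standard deviations. Putting b in place of d gives the chance that a two-sided 5% t test rejects:

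| b (assumed) | 12 per arm | 15 per arm |
|---|---|---|
| 0 | 5.0% | 5.0% |
| 0.1 | 5.6% | 5.8% |
| 0.2 | 7.6% | 8.3% |
| 0.3 | 10.8% | 12.5% |
| 0.4 | 15.5% | 18.5% |
| 0.5 | 21.6% | 26.2% |

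The plan specifies an ANOVA, so the t test is a simplification. The table shows how the error rate would respond to a shift. It is not evidence that a shift will occur.

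**The case against.** The strongest reply is that the protocol claims only what it does. It says that the assessor is blinded and that the group is kept from one researcher; it nowhere says that patients or therapists are blinded. Patients cannot be masked to being taught by video or in person, and self-report is the proper way to measure pain. Both arms receive the same conventional treatment, number of sessions and exercises, with no sham or untreated arm, so any difference in expectation may be small.

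Much of this stands, and it rules out several stronger readings that a reader might infer.

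- **That the label is false.** The documents do not show this. It has content for the walk and gait tests, and a masked researcher may also hand out, measure or score the self-report forms.
- **That patients answer in front of the physiotherapist who taught them.** The session timing leaves this possible, but no section says who is present or who collects the forms. The baseline and third-month readings need not involve the treating therapist, and Item 12a does not say that session readings drive the group comparison.
- **That the same person assigns, treats and assesses.** Names have been removed from Items 8a and 11a, so separation of staff can be neither confirmed nor denied. The point does not rest on it.
- **That the results will favour multimedia teaching.** Nothing states what patients are told to expect, and the consent pages are not available. Bias could run either way or be negligible.

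What the reply does not answer is that the label is given without limit by outcome, that the rater of the sizing outcome is unblinded, and that disclosure to the masked researcher is left open.

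**Conclusion.** The point holds as a limited one. Masking the researcher does not blind the rater of pain, disability or adherence, and the single stated measure does not prevent a patient revealing the teaching method, which also puts the walk and gait tests at risk. It rests on one inference, that patients recognise how they were taught, and on the absence of any other stated measure. It is a matter of risk of bias and of how the results may be described. It changes neither the sample size nor the analysis, and the bias cannot be quantified from the documents. Priority is low, but the remedy is cheap enough to be worth making.

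**What to change.** Revise Item 11a as follows, and align Item 3a with it.

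1. Before each assessment, instruct patients not to mention how they were taught.
2. At baseline, end of treatment and month 3, have patients complete the pain VAS, Oswestry, EARS and home-exercise VAS (each where it is due) themselves, out of sight of the treating physiotherapist, and return them to the masked researcher.
3. State that patients and treating physiotherapists are not blinded. Limit the assessor-blinded claim to the walk and gait tests and to the handling and scoring of forms. Interpret the pain, disability and adherence results as unblinded self-report.

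The cost is a weaker blinding claim and a little extra form handling; no new staff are needed. I would not extend step 2 to every session: with up to 16 sessions and two pain readings at each, that is 16 × 2 = 32 pain forms per patient, or 32 × 30 = 960 for the trial, for a doubtful return.
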